1.0 Synopsis

Title	SARS-CoV-2 transmission in Belgian primary schools of the Federation Wallonie - Bruxelles. An epidemiological pilot study.
Study design	Interventional prospective SARS-CoV-2 infection study.
Study duration	Autumn – winter 2020-2021
General objective	Description and quantification of transmission dynamics of SARS-CoV-2 in primary schools.
Specific objectives	
To assess the role of children attending primary school in the spread of SARS-CoV2 during the 2020-2021 pandemic
 
 • To assess transmission from asymptomatic infected children to other children attending the same school • To assess transmission from asymptomatic infected children to adults (parents and teachers) • To assess transmission from asymptomatic infected adult within the school environment to a child • To assess if a laboratory confirmed case in a classroom has been infected outside the school
Study hypothesis	The investigators hypothesize that children are less likely to become infected in the school environment, compared to the household or outside the school setting. Primary schools do not play a major role in SARS-CoV-2 spreading. They hypothesize that incidence level in schools is mainly a consequence of community transmission ie. the incidence level in households and that the secondary attack rate in schools remains at least 5 times lower than the transmission level in households.
Outcomes	
 • Infection of a child with SARS-CoV-2 secondary to a classmate • Infection of an adult with SARS-CoV-2 secondary to a child • Infection of a child with SARS-CoV-2 secondary to an adult within the school • Infection of a child with SARS-CoV -2 secondary to a household contact or outside the school
Exploratory outcome	Phylogenetic analysis of the SARS-CoV-2 in positive salivary tests by a Whole Genome Sequencing (WGS) test. The aim of this exploratory outcome is to determine potential linkages between cases.

Study participants/numbers of participating schools	
All Belgian primary schools of the Federation Wallonie – Bruxelles that have organized a full resumption of school activities with the control measures recommended by the government, are eligible for the study.
 
Inclusion criteria All children and school attenders from selected schools will be invited to participate.
 
Exclusion criteria Refusal to provide written informed consent before enrolment
 
Sampling procedure Each participating primary school will be considered as a cluster. Eight schools will be chosen by purposive sampling on three criteria: either high (≥ 2 classes per grade) or low size of the school, a school within an area with either a high or a low incidence of SARS-CoV-2 during April 2020, the first wave of covid-19 in Belgium, and a school with either a high or a low socioeconomic level (Belgian 20-point-scale ISE index >14 or <6). As direct partners in the project, physicians in charge of health promotion in schools (PSE teams) will select schools.

Study description	
Inclusion visit All participants (children and adults school attenders) will be tested at the inclusion day with
 
 - A salivary SARS-CoV2 test - A rapid serological test by finger prick (AVIOQ[®]) to determine the seroprevalence of SARS-CoV-2 
All participants (children and adults school attenders) will be invited to fill a questionnaire on an electronic format when possible or with a paperback part if not, depending on parents' convenience.
 
Follow-up visits During six consecutive weeks, all participants will be tested once a week with a salivary test. During six consecutive weeks, all participants will be invited to complete a follow-up questionnaire to assess any symptom compatible with a SARS-CoV-2 infection or a contact with a confirmed SARS-CoV-2 case or a travelling return from a risk area.

Endpoints	
 - Time varying number and proportion of children infected with SARS-CoV-2 secondary to an infected classmate (transmission rate inside school but from a child to a child). - Time varying number and proportion of adult school-attenders infected with SARS-CoV-2 secondary to an asymptomatic infected child (transmission rate inside school but from a child to an adult); - Time varying number and proportion of children infected with SARS-CoV-2 secondary to an infected adult school attender (transmission rate inside school but from an adult to a child);

	
 - Time varying number and proportion of children infected with SARS-CoV -2 secondary to a household contact or outside the school (transmission rate from outside school).
Statistical analyses plan	
Sample size determination
 
As a pilot study, no formal sample size calculation was performed. The expected number of children is 2400, the expected number of adult school attenders is 200, and the expected number of classes is 72.
 
Initial incidence and then secondary attack rates will be calculated and compared between gender, across age, and between the three kinds of schools using Poisson or Binomial negative regression if overdispersion. Analyses will be weighted to correct for cluster effect of classes (ICC=0.09).

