4.3 Selection of participating schools

All Belgian primary schools of the Federation Wallonie – Bruxelles that have organized a resumption of school activities with the social control measures recommended by the government, are eligible for the study. All children and school attenders attending included schools will be eligible to participate.

Each participating school will be considered as a statistical cluster because children within a school share more correlation together than with children from other schools (children are not an independent and identically distributed (i.i.d.) sample) and an intraclass coefficient (ICC) of 9% will be used in analysis.

We will enrol schools according to the following three criteria:

- School size: small school versus a large one

- Incidence of Sars-CoV-2 infection during the first wave of the pandemic in April 2020
 - Regions/cities with a low incidence (from 1.5 to 4.9 per thousand inhabitants on May 6th, 2020)
 - Regions/cities with a high incidence (from 5.0 to 7.5 per thousand inhabitants on May 6th, 2020)
- Socio-economic level of the school: low socio-economic level versus high level, based on ISE that is an official Belgian 20-point-scale index for all schools of the Federation Wallonie-Bruxelles (FWB).

Crossing those three criteria leads to eight categories of schools and one school of each category will be sampled

- Small school - very low incidence city - low socio-economic level
- Small school - very low incidence city - high socio-economic level
- Small school - very high incidence city - low socio-economic level
- Small school - very high incidence city - high socio-economic level
- Large school - very low incidence city - low socio-economic level
- Large school - very low incidence city - high socio-economic level
- Large school - very high incidence city - low socio-economic level
- Large school - very high incidence city - high socio-economic level

According to the definition of the FWB, investigators consider a small school a school with less than 300 children enrolled in the school and a large one a school with more than 300 children.

To determine regions with the highest and lowest incidence of SARS-CoV-2 infection during the first pandemic wave in Belgium investigators will refer to the epidemiological reports of Sciensano: <https://covid-19.sciensano.be/fr/covid-19-situation-epidemiologique>

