7.0 Statistical analyses plan

7.1 Sample size and statistical analysis

As a pilot study, no formal sample size determination was performed. The expected number of children is 2400 (4 times 200 plus 4 times 400), the expected number of adult school attenders is 200, and the expected number of classes is 72. With an incidence around 0.5-1%, the expected number of cases is 120-240. Initial incidence and then secondary attack rates (as transmission estimator) will be calculated and compared between gender, across age, and between the three kinds of schools using Poisson or Binomial negative regression if overdispersion. Characteristics of classes will be compared between schools using ANOVA with F-tests for continuous variable and chi-square or Fisher exact tests for discrete variables. Any significant difference will be considered for correlation with incidence rates (per classes) and attack rates within the Poisson or Binomial negative regression. A cluster effect (Rho = 1.09 or ICC=0.09) will be assessed for weighting data analysis. Estimates will be presented with their 95% Confidence interval. Differences will be presented as absolute and relative differences.

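### A fixed ICC=0.09 weight on every analysis can count class clustering twice: up to about 2 times too wide CIs on negative binomial class counts, and also for gender within class

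*Combined protocol and SAP*

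**What the plan says.** The synopsis (section 1.0, Statistical analyses plan) compares initial incidence and secondary attack rates by gender, age and kind of school, and names the method in two adjoining sentences: "Poisson or Binomial negative regression if overdispersion. Analyses will be weighted to correct for cluster effect of classes (ICC=0.09". The second of these covers all analyses and makes no exception for the negative binomial.

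Section 7.1 repeats the model choice and adds a step for class characteristics: "Any significant difference will be considered for correlation with incidence rates (per classes) and attack rates within the Poisson or Binomial negative regression". Its sentence on clustering is softer: "A cluster effect (Rho = 1.09 or ICC=0.09) will be assessed for weighting data analysis".

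Section 4.3 puts the cluster at another level: "Each participating school will be considered as a statistical cluster". It attaches the same 9% to the school. The sampling paragraph of the synopsis also names the school as the cluster.

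Nowhere do the documents give the unit of analysis (child, class, or class by week), a formula for the weight, or a rule on whether the weight is dropped once the negative binomial is in use.

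**The concern.** In a regression of class totals, correlation between children of one class shows up as extra variation between classes. That is the overdispersion that triggers the switch to the negative binomial, and the dispersion parameter then carries it into the standard errors. A further weight for class clustering charges the same variance again.

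The class-count path is a realistic one. Room size, ventilation and lunch space are collected once per class (section 5.1), so they can only be compared between classes, and section 7.1 speaks of incidence per class at that step. On this path real differences between classes could be reported as no difference.

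A blanket weight also ignores which way clustering acts. For a contrast between classes it widens the true uncertainty. For a contrast within classes, such as boys against girls, it does not, so a design-effect weight there is too large whatever the model.

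**Working it through.** **Inputs.** Section 7.1 gives "The expected number of children is 2400 (4 times 200 plus 4 times 400") and says that "the expected number of classes is 72". The ICC is 0.09 (synopsis, sections 4.3 and 7.1). The weight 1/DEFF is an assumption, since the plan gives no formula.

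**The plan's own figures.** 4 × 200 + 4 × 400 = 2400. Assuming six grades, with one class per grade in small schools and two in large ones, 4 × 6 × 1 + 4 × 6 × 2 = 72. Both agree. Mean class size is m = 2400/72 = 33.3.

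**Size of the weight.** DEFF = 1 + (m − 1) × ICC, and the interval width changes by √DEFF.
- Full participation: 1 + 32.3 × 0.09 = 3.91; √3.91 = 1.98.
- Assumed participation of 30%, 50%, 70% (m = 10, 16.7, 23.3): DEFF = 1.81, 2.41, 3.01; factor 1.35, 1.55, 1.73.
- Weight read as 1.09: √1.09 = 1.04. The formula gives 1.09 only at m = 2.
- School as cluster (mean m = 2400/8 = 300): DEFF = 1 + 299 × 0.09 = 27.9; factor 5.28.

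**Between-class contrast, by simulation.** Beta-binomial counts in 72 classes of 33, ICC 0.09, one class-level covariate, no school effect, about 1,500 datasets per row. The 5% and 10% risks correspond to the plan's 120 to 240 cases among 2400 children; 1% is a low-incidence check. Entries after the second column are median standard errors of the log rate ratio.

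| Cumulative risk | SD of estimates | Poisson | Poisson, weighted | Neg. binomial | Neg. binomial, weighted |
|---|---|---|---|---|---|
| 1% | 0.888 | 0.449 | 0.885 | 0.808 | 1.591 |
| 5% | 0.364 | 0.188 | 0.371 | 0.360 | 0.709 |
| 10% | 0.238 | 0.131 | 0.258 | 0.248 | 0.488 |

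- One correction works. The unweighted negative binomial gives 0.91 to 1.04 of the true SD, with coverage 94% to 96%. Weighted Poisson gives 1.00 to 1.08, with coverage from 97% to above 99%.
- Both corrections together give 1.79, 1.95 and 2.04 times the true SD (before rounding), with coverage about 100%.
- No correction gives 0.51 to 0.55 of the true SD, with coverage about 70%.

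**Does the switch happen?** On class totals the Pearson dispersion was 2.89 to 3.48. In separate runs a likelihood ratio test detected overdispersion in 91% to 95% of datasets at 0.75% incidence and in about 100% at 3% to 7.5%. On child-level 0/1 records the dispersion was 0.90 to 0.99 despite the ICC of 0.09. There the negative binomial is not triggered and its dispersion parameter absorbs no class variation.

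**Gender within class.** True SD 0.188 at 5% risk and 0.123 at 10%. Unweighted Poisson: 0.188 and 0.133, about right. Weighted Poisson: 0.371 and 0.261, which is 0.371/0.188 = 1.97 and 0.261/0.123 = 2.12 times the true SD. A negative binomial on class-by-gender cells is also too wide (0.284 and 0.196).

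**Illustration of the cost.** With 36 against 36 classes and a rate ratio of 2, adding the weight to the negative binomial lowers power from 49% to 3% at 5% risk, and from 76% to 15% at 10% (400 to 600 datasets per scenario). The split and the rate ratio are chosen here; the plan sets no target.

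**The case against.** The strongest reply is that the plan never commits to the double correction. The unit of analysis is open. Gender and age comparisons point to child-level data, and incidence per class is mentioned only once, at the class-characteristics step. Section 7.1, the fuller text, says only that a cluster effect will be assessed. The weight could mean 1.09. Weights rescaled to mean 1 would do no such harm, although with equal class sizes they would correct nothing either. Enrolment needs consent and assent, so full participation is unlikely. The study is a pilot without a power target.

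Most of this stands. A reader might infer that the plan definitely corrects twice and that its intervals are in general twice too wide. The documents do not support that: it is one branch, and the factor depends on a weight formula they do not state.

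A reader might also infer that the weight can simply be struck out. That is wrong too. For class-level contrasts on the Poisson or child-level paths it is the only correction, and without a replacement coverage is about 70%.

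Nor does class-level dispersion settle clustering as a whole. It treats classes of one school as independent, while section 4.3 names the school as the cluster.

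What the reply does not remove is that the synopsis wording covers all analyses, that an analyst who follows it on class counts applies both corrections, and that the gender result does not depend on the negative binomial at all.

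**Conclusion.** The concern holds in conditional form. If class counts are fitted by negative binomial and also weighted by 1/DEFF with ICC=0.09, class clustering is counted twice and 95% intervals are up to about 2 times too wide: 1.98 at full participation, 1.35 to 1.73 at an assumed 30% to 70%, and 1.04 if 1.09 is the weight. For gender the blanket 1/DEFF weight about doubles the standard error even under Poisson.

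These figures assume class as the cluster, equal class sizes, a true ICC of 0.09 and no school effect. They do not rest on the expected 120 to 240 cases, a range that 0.5% to 1% of 2400 does not give directly (12 to 24, or 72 to 144 over six weeks): at 1% risk the simulated factor is still 1.79. The power figures do rest on 5% to 10% risk.

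This is more than missing detail. The rule as written gives wrong error bars on two plausible paths, and it leaves the analyst to choose after seeing the data between intervals that can differ about twofold.

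**What to change.** Replace the fixed-ICC weighting sentences in the synopsis and section 7.1 with one clustering mechanism per model, estimated from the data, and state the unit of analysis for each comparison:

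- Class-count models (class characteristics): negative binomial with log(children tested) as offset.
- Child-level models (gender, age): a class random effect or class-robust standard errors. Gender belongs here, not in class-by-gender counts.
- No additional ICC=0.09 design-effect weight for class in either.

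Reconcile the cluster level between the weighting sentence of the synopsis (class) and its sampling paragraph and section 4.3 (school), and bring the 9% in section 4.3 into line. Account for school separately, for example with a school term in the class-characteristic, gender and age models. The comparison between kinds of schools needs its own statement: kind is constant within a school and there are only eight schools, so a fixed school term cannot be used there.

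The cost is small: wording only and no new data. The drawback is that clustering estimated from the data will be imprecise if cases are few.

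### One class-cluster weight is planned for every comparison, although gender varies within classes; under the usual inverse design-effect weight the gender interval would be about 1.3 to 2 times too wide

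*Combined protocol and SAP*

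**What the plan says.** The statistical paragraph of the synopsis (section 1.0) names the comparisons: "Initial incidence and then secondary attack rates will be calculated and compared between gender, across age, and between the three kinds of schools". The next sentence gives one correction for all of them: "Analyses will be weighted to correct for cluster effect of classes (ICC=0.09").

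Section 7.1 repeats that the rates "will be calculated and compared between gender, across age, and between the three kinds of schools using Poisson or Binomial negative regression if overdispersion", and adds later: "A cluster effect (Rho = 1.09 or ICC=0.09) will be assessed for weighting data analysis". This is softer (the effect is to be assessed), gives two figures, and names no cluster level.

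Section 4.3 puts the clustering elsewhere: "Each participating school will be considered as a statistical cluster", and "an intraclass coefficient (ICC) of 9% will be used in analysis".

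No section gives a formula for the weight, says whether it enters as a precision weight or with robust standard errors, or treats child-level factors differently from class-level or school-level ones.

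**The concern.** The familiar design effect, 1 + (m − 1) × ICC, is the variance inflation for a factor that takes one value for a whole cluster, or for an overall rate. It is not the inflation for a factor that varies inside the cluster. Boys and girls sit in the same classes. If a class has a raised risk that both sexes share, that risk appears on both sides of the gender contrast and largely cancels.

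A single weight built from the class design effect would therefore overstate the uncertainty of the gender comparison. A real difference between boys and girls could be reported as not shown. The same applies to any other child-level characteristic that is mixed within classes. The direction is the opposite of the usual clustering problem, where ignored correlation makes intervals too narrow.

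**Working it through.** **Inputs from the documents.** Section 7.1: "The expected number of children is 2400 (4 times 200 plus 4 times 400"), and "the expected number of classes is 72". ICC 0.09 is in the synopsis and in sections 4.3 and 7.1; Rho 1.09 is in section 7.1. The counts reproduce: 4 × 200 + 4 × 400 = 2400 children. With six grades, one class per grade in small schools and two in large ones (assumed), 4 × 6 + 4 × 12 = 72 classes. Mean class size is m = 2400/72 = 33.3.

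**Class design effect.** 1 + (33.3 − 1) × 0.09 = 3.91. A precision weight of 1/3.91 multiplies every standard error by √3.91 = 1.98.

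**What the gender contrast needs.**
- Shared class risk, sexes balanced within class: inflation is about 1 − ICC = 0.91. The weighted interval is too wide by √(3.91/0.91) = 2.07, or by 1.98 against an inflation of exactly 1.
- Fully sex-specific class risk: the cluster is in effect half a class, so inflation is 1 + (33.3/2 − 1) × 0.09 = 2.41. The weighted interval is too wide by √(3.91/2.41) = 1.27.

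**Other readings of the weight** (standard-error multiplier for gender):

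| Reading | Multiplier |
|---|---|
| 1/3.91 precision weight, class as cluster | 1.98 |
| Same, 50–90% participation (assumed; m = 16.7–30) | 1.55–1.90 |
| Rho = 1.09 as the variance multiplier | √1.09 = 1.04 |
| School as cluster, m = 2400/8 = 300 | √27.91 = 5.28 |
| Constant weights with class-robust standard errors | no inflation |

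**Simulation.** 20,000 studies per scenario; 72 classes of 33; beta-distributed class risk with ICC 0.09; gender at random within class; 5% cumulative incidence (120 cases); no gender effect; test at |z| > 1.96.
- Shared class risk: the true SD of the log rate ratio is 0.183. The unweighted standard error is 0.186, the class-clustered one 0.178 and the 1/3.91-weighted one 0.368. The last is 0.368/0.183 = 2.0 times too large, and its type I error is near 0% (about 6% class-clustered, about 4% unweighted).
- Sex-specific class risk: the true SD is 0.286. The weighted standard error of 0.368 is 0.368/0.286 = 1.29 times too large (type I error 0.9%). The unweighted test rejects in 20%; the class-clustered test stays near 6%.
- Few cases (0.75% incidence): the uncorrected class-clustered test has size of about 9%. With sex-specific clustering and few cases, the unweighted test rejects in about 17%.

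**What the width means.** Take an assumed rate ratio of 1.5 with 120 cases split 72 to 48. The standard error is √(1/72 + 1/48) = 0.186, and the 95% interval is 1.04 to 2.16. It becomes 1.02 to 2.20 with a multiplier of 1.04, and 0.73 to 3.09 with 1.98.

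**Power, as illustration only.** For an assumed rate ratio of 2 with 120 cases and shared class risk, simulated power is 96% with class-clustered standard errors and 36% with the 1/3.91 weight. A two-proportion formula with sample size divided by 3.91 gives 47%.

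**The case against.** The strongest reply is that the 1/3.91 weight is nowhere in the documents. This stands. A reader might infer that the gender interval, as planned, is twice too wide; the documents do not support that as a fixed consequence. The multiplier runs from none to about fivefold, depending on what the authors mean. What the synopsis does fix is one class-level correction for all comparisons, and the inverse design effect is the usual way to turn a known ICC into a weight.

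A reader might also infer that power collapses. The plan calls the study a pilot with no formal sample size, and states no power, significance level or gender effect, so there is no planned power to lose. The rate ratios above are assumptions. So is the case count: the plan's 120–240 cases do not follow from 0.5–1% of 2400, which is 12–24 per test round and 72–144 over six rounds. With only 12–24 cases, power for a rate ratio of 1.5 is about 10–17% even without weighting.

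Third, one might conclude that gender needs no clustering correction at all. That holds only if boys and girls share the class risk. The documents do not describe contact by sex, and the first outcome is infection from a classmate. With sex-specific clustering some correction is needed, although the blanket weight is still too large.

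Finally, gender is in no objective, hypothesis, outcome or endpoint, and the error would be conservative. This limits the weight of the point. Nor does the simulation cover secondary attack rates or the negative binomial option, so its sizes apply to incidence under a Poisson standard error.

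**Conclusion.** The point holds in conditional form. The plan applies one class-cluster correction to comparisons that need different ones, and does not define the correction. Under an inverse design-effect weight of 1/3.91, the gender interval is about 2 times too wide with shared class risk and about 1.3 times too wide with fully sex-specific class risk. It is about 4% too wide if 1.09 is the multiplier (shared class risk), and about fivefold if the school is the cluster. These sizes assume full participation, equal class sizes and an even mix of the sexes.

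This does not show that the study's main transmission results are affected. The consequence is limited to gender and other child-level factors that vary within classes. It is worth correcting because a standard model gives each covariate its own variance and removes the dependence on how the weight is read.

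**What to change.** In the synopsis and section 7.1, replace the fixed ICC weight with a child-level Poisson or negative binomial model with a class random effect, or with class-clustered standard errors. Report the gender ratio and difference, with 95% intervals, from that model. Bring the cluster level in section 4.3 into line with it, and drop Rho = 1.09 or define it.

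A class random intercept alone relies on boys and girls sharing the class risk; class-clustered standard errors do not. With very few cases, use the class random effect or a small-sample-corrected sandwich standard error. The uncorrected sandwich is too small there, and the unweighted standard error is anti-conservative if clustering is sex-specific.

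The cost is one or two sentences in each place, standard software and no new data. The drawbacks are slightly more analysis work and possible convergence problems when cases are few.
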